6.7.5 Quality of Life Survey

SF-36v2 Health Survey will be completed.

6.7.6 Wound Tissue Sample

Two tissue sections of at least 2mm will be reserved from debridement material for later analysis. ***If debridement at the final follow-up is not medically necessary it should be omitted.***

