
Study Design and Procedures
	
This is a multi-center post-market, single-arm, prospective follow-up study
 
Assessment and Roll-in Phase
 
Subjects will be recruited by the treating physicians, screened for eligibility, invited to participate in the study and provide informed consent. The subject's demographics, medical history, co-morbidities and wound characteristics will be documented and the subject will complete a SF-36 quality of life questionnaire. Subject will be instructed on proper nutrition.
 
Wound will undergo sharp debridement, be traced, photographed, and dressed per standard of care. Two tissue sections of at least 2mm will be retained for histological analysis. Subject will be fitted with and instructed on an offloading device. Subjects will return for MIRODERM treatment in two weeks.
 
Treatment Phase
 
On treatment day, wound will undergo sharp debridement, be traced, photographed and MIRODERM Biologic Wound Matrix will be applied. After treatment, subjects will be considered enrolled into the trial. Details of treatment will be documented.
 
Subject will present weekly for the next twelve weeks. The dressing will be changed and may undergo further MIRODERM treatment if indicated. The wound will be traced and photographed. Physician will document their assessment on whether the wound is 100% closed.
 
Subjects whose wound is completely closed at or prior to 12-weeks post-treatment, will be instructed to return 1-week following for a confirmation visit. Subjects whose wound is not assessed as closed by 12-weeks post-treatment, will have two tissue sections of at least 2mm collected, complete a quality of life assessment, and will then be discontinued per protocol.
 
Confirmation Phase
 
Subject will complete a quality of life assessment and have their wound area photographed. Physician will confirm the wound is still closed and the subject will be discontinued per protocol. If wound has reopened subject will return to the treatment phase.

Subject Participation
	
Subjects can be expected to reasonably participate in the study for a minimum of 9 weeks and a maximum of 15 weeks depending treatment course.

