5 RISK EVALUATION

5.1 Potential Risks to Study Patients

MIRODERM wound matrix is a cleared wound care product and will be used in accordance with approved indications and instructions for use (K140510 and K143426). As an observational, post-market study of a commercialized device for approved indications, the risk to a patient participating in this study is not fundamentally different than the risks this patient would encounter undergoing treatment with a porcine derived biologic wound matrix and not participating in this study. Thus, the only risk unique to this study would be inadvertent disclosure of protected health information.

There are risks, not directly associated with study participation, associated with treatment which may include but are not limited to:

- Sensitivity or allergic reaction to porcine material
- Infection
- Additional tissue damage during sharp debridement
- Cellulitis
- Osteomyelitis

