If wound has not closed, the dressing will be changed (subsequent to any needed treatment as described in the above paragraph) and the subject will return the following week. If the wound is healed subject will return for a confirmation visit one week later. If, after 12 weeks, the wound is not healed, subject will complete a SF-36 quality of life survey, two tissue sections of at least 2mm from the wound area will be collected and the subject will be discontinued from the study per protocol.

Confirmation Phase

Subject will complete a quality of life assessment and have their wound area photographed. Physician will confirm the wound is still closed and the subject will be discontinued per protocol. If wound has reopened subject will return to the treatment phase.

Subjects whose wound has been assessed closed will return for a confirmation visit. The wound will be assessed for closure. If the wound is still closed, the wound area will be photographed, the subject will complete a SF-36 quality of life survey and be discontinued from the study per protocol. If wound has reopened, subject will return to the follow-up phase at the appropriate post-treatment week continuing there until wound closure or through 12 weeks of follow-up as described in “Treatment Phase” above.

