6.10.15 Wound Tissue Sample

During initial debridement and with subjects whose wounds do not close after 12 weeks of follow-up, two tissue sections of at least 2mm from the wound area will be obtained. Each tissue sample will be placed into formaldehyde filled 5 ml plastic sample tubes provided. Using a standard "Sharpie" marker, each tube shall be labeled with subject number and date acquired. Tubes will be stored at room temperature until collected by the sponsor.

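### The exit tissue sample is unconditional in four places but depends on needed debridement in section 6.7.6, and the risk statement in section 5.1 agrees only with 6.7.6

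*Combined protocol and SAP*

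**What the plan says.** Four places describe the exit sample without reference to debridement.

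- **Synopsis, Treatment Phase.** Subjects not assessed as closed by 12 weeks "will have two tissue sections of at least 2mm collected, complete a quality of life assessment, and will then be discontinued per protocol".
- **Section 6.1.** If the wound is unhealed after 12 weeks, "two tissue sections of at least 2mm from the wound area will be collected".
- **Table 1 (section 6.3).** The tissue sample is marked at Final Follow-up, and the footnote's only condition is incomplete healing. Sharp debridement is a separate row, shown as needed after the treatment visit.
- **Section 6.10.15.** At initial debridement, and for wounds not closed after 12 weeks of follow-up, "two tissue sections of at least 2mm from the wound area will be obtained".

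Section 6.7.6, the instruction for the 12-week visit, differs: "Two tissue sections of at least 2mm will be reserved from debridement material for later analysis". It continues, with emphasis in the text: "If debridement at the final follow-up is not medically necessary it should be omitted".

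Section 5.1 states that "the only risk unique to this study would be inadvertent disclosure of protected health information". It lists tissue damage from sharp debridement among treatment risks that it separates from study participation, and it does not mention tissue sampling.

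**The concern.** A site working from Table 1 or section 6.10.15 sees no exception. It could take tissue from an open diabetic foot ulcer, for research only, in a subject with no clinical need for debridement. A site working from section 6.7.6 would take nothing from the same subject. The protocol has no rule on which section prevails.

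Two things are at stake. The first is patient safety: section 5.1 recognises no physical risk specific to the study, which is consistent with tissue being a by-product of needed care but not with tissue taken for research alone. The second is the histology objective in section 4.3. Conditional sampling gives exit tissue only from unhealed wounds that were debrided, a restriction the protocol does not mention. If sites differ in the rule they follow, the selection also differs by site.

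**Working it through.** **1. The passages side by side.** Take a subject unhealed at the 12-week visit.

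| Debridement at that visit | Synopsis, 6.1, Table 1, 6.10.15 | 6.7.6 | Statement in 5.1 |
|---|---|---|---|
| Needed | Sample | Sample, from debridement material | Consistent if the tissue comes from that material |
| Not needed | Sample | No sample | Incorrect under the four places; consistent under 6.7.6 |

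The rules differ only in the second row.

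**2. Can 6.7.6 be read another way?** The pronoun in its last sentence could refer to the debridement or to the sample. Either way, without debridement there is no debridement material, so no sample.

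**3. Can 6.10.15 be read as carrying the condition?** It mentions debridement only for the initial sample. For the exit sample its only condition is that the wound has not closed.

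**4. Size.** The plan gives no figure for exit samples. The closure rates used here are the illustrative ones in the sample size justification (section 7). Recomputing its Clopper-Pearson limits at n = 50 reproduces the plan's values: 13.8%-39.3%, 35.5%-64.5% and 60.7%-86.2% at 25%, 50% and 75%.

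Let N be the number enrolled, c the closure rate, and q the share of unhealed subjects not needing debridement at the final visit. With no early exits:

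affected = N × (1 − c) × q

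The documents do not give q, so it is taken from 0 to 1. At q = 1 and N = 50:

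- c = 75%: 50 × 0.25 = 12.5, about 12-13
- c = 50%: 50 × 0.50 = 25
- c = 25%: 50 × 0.75 = 37.5, about 37-38

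At the enrolment ceiling of 65 the same bounds are 65 × 0.25 = 16.25, 65 × 0.50 = 32.5 and 65 × 0.75 = 48.75. At q = 0 the count is zero in every case. Early exits for infection, osteomyelitis, withdrawal, loss to follow-up or death (section 6.2) lower these bounds.

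**The case against.** The best reply is that section 6.7.6 is the operative instruction for this visit, and its limit is emphasised. The synopsis and section 6.1 are overviews. They treat the entry sample the same way, saying only that sections are retained, while section 6.5.6 supplies the source as debridement material. On that view the overviews omit the source and the visit sections fill it in. The Table 1 row showing debridement as needed can be read to fit, and section 5.1 points the same way.

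This is plausible for the synopsis and section 6.1, and it may reflect what was intended. It does not dispose of section 6.10.15, a procedure section with the same title as 6.7.6, which ties only the initial sample to debridement. Nor does the Table 1 footnote carry the condition. Without a precedence rule, a site could follow the written text and still take tissue that 6.7.6 would not.

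The objection does rule out several stronger inferences that a reader might draw:

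- **That the protocol prescribes a separate research biopsy.** No passage describes a punch, an excision or any other separate procedure. The conflict leaves room for research-only sampling; it does not describe it.
- **That consent is deficient.** The consent form is not in the reviewed text, and section 6.10.1 says it will outline potential risks. No claim is made about its wording.
- **That exit histology becomes uninterpretable.** The aim is exploratory, and section 7 specifies no histology analysis. Exit tissue is planned only for unhealed subjects, so it could not by itself compare healed with unhealed wounds. The roll-in sample, planned for both groups, is untouched.
- **That 12-13, 25 or 37-38 subjects are affected.** Those numbers count all unhealed subjects at n = 50, so they are upper bounds.

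**Conclusion.** The inconsistency stands. Four places require the exit sample from every subject unhealed at 12 weeks, and section 6.7.6 does not. Section 5.1 is consistent with 6.7.6 but would be incorrect for any subject sampled under the other four places without a clinical need for debridement.

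The affected group is the unhealed subjects not needing debridement at the final visit. It lies between zero and the bounds above, which rest on the plan's illustrative closure rates and on no early exits. The statistical consequence is confined to the exploratory histology objective: exit tissue that is selected and, if sites follow different rules, inconsistently sampled. The primary endpoint does not depend on it. The point should be corrected because it bears on patient safety and the remedy is simple.

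**What to change.** The sponsor should choose one rule for the exit sample and state it identically in the synopsis, section 6.1, Table 1 with its footnote, section 6.7.6 and section 6.10.15, then align section 5.1 with it.

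- If sampling depends on debridement, add that condition wherever it is missing. Describe exit histology as covering only unhealed wounds that were debrided, and report the number sampled beside the number unhealed.
- If sampling does not depend on debridement, revise section 6.7.6 and list the sampling in section 5.1 as a study-specific risk.

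Which clinical rule applies is for the sponsor to decide. The cost is protocol wording and, depending on the choice, fewer exit samples or a revised risk statement. Sample size and the primary analysis do not change.

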6.8 Confirmation Visit (1 week after complete closure or Visit 15; Week 16)

6.8.1 Wound Closure Assessment

Wound will be assessed for closure. If wound is still closed subject will continue to 6.8.2 below. ***If it is determined that the wound is reopened,*** subject will have wound assessed (6.7.2) and treated as needed (6.7.3). Subject will continue in the follow-up phase (6.7) until wound is closed or 12 weeks of follow-up have been completed.

6.8.2 Wound size documentation

The wound area will be photographed.

6.8.3 Quality of Life Survey

SF-36v2 Health Survey will be completed.

6.9 Study Exit

Subjects will be discontinued from the study per protocol. Under the following circumstances:

- Subject's index wound has been determined to be fully closed and remains closed at their 1-week follow-up confirmation
- Subject had completed their 12-week post-treatment follow-up and their index wound has not completely healed
- Subject presents with osteomyelitis of the study DFU or an infection of the study DFU
- Subject voluntarily withdraws consent.
- Subject lost-to-follow-up
- Subject death

When a subject is study exited, patients are no longer considered participants in the study and have no further obligations under the protocol. patients may undergo continued care as deemed appropriate by physician of record.

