4.3 Secondary Objectives

Some secondary objectives include but are not limited to:

- Describe the time course to full wound closure
- Determine the subjects' quality of life score before and after treatment
- Characterize the safety profile of MIRODERM and the procedure
- Explore the histological characteristics of those who successfully heal and those who don't

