6.6.3 Wound assessment and size documentation

Wound will be assessed for gross dimensions and infection. If an infection is present an AE form should be completed and ***the subject will be discontinued from the study.***

The area of the wound will be documented using the E-Z Graph Wound Assessment System and photography.

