6.7.2 Wound assessment and size documentation

Wound will be assessed for gross dimensions and infection. If an infection is an AE form should be completed and ***the subject will be discontinued from the study.***

The area of the wound will be documented using the E-Z Graph Wound Assessment System and photography.

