14 ADVERSE EVENT AND SAFETY REPORTING

14.1 Definitions

Adverse Event

An adverse event (AE) is any untoward medical occurrence in a subject; it does not necessarily have to have a causal relationship with the device or the procedure. An AE can therefore be any unfavorable and unintended sign (including abnormal laboratory finding), symptom, or condition whether or not considered related to device or procedure.

Serious Adverse Event

A serious AE (SAE) is an AE that leads to 1 of the following conditions:

- Death
- Life-threatening illness or injury
- Serious deterioration in the health of the subject that results in 1 of the following situations:
 - Permanent impairment of a body structure or a body function
 - Medical or surgical intervention to prevent permanent impairment to body structure or body function
 - Inpatient hospitalization or prolongation of existing hospitalization
 - Fetal distress, fetal death, or a congenital abnormality or birth defect

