14.2 Reporting of Adverse Events

For the purposes of this study, only events that occur after MIRODERM treatment can be considered AEs. Likewise, reportable AEs will be limited to AEs which are 1) definitely related to, or 2) likely related to, the study wound or treatment. Reportable events include but are not limited to:

- Cellulitis
- Osteomyelitis
- Wound recurrence
- A substantial increase in ulcer size
- Wound infection
- Debridement related AEs

AEs and follow-up information will be reported to the IRB according to the individual IRB's policies

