14.3 Adverse Event Assessments

All AEs, which are 1) definitely related to, or 2) likely related to, the study ulcer or treatment will be documented on an AE form and assessed by the physician with respect to relatedness and severity.

Each AE record will include a description of the event, date of onset, date of resolution, severity, treatment as applicable, and relationship to study device. Each AE must be recorded separately.

Severity will be assessed using the following definitions:

Mild: Aware of sign or symptom, but easily tolerated

Moderate: Discomfort enough to cause interference with usual activity

Severe: Incapacitating with inability to work or do usual activity

Relationship to the study treatment or the study device will be assessed by the investigator using the following definitions:

Likely: A temporal relationship exists between the event onset and the study procedure or device, and appears with some degree of certainty to be related based on the event symptoms and the nature of the study procedure or device. It cannot be readily explained by the subject's clinical state or concomitant therapies.

Definitely: Strong evidence exists that the study procedure or device caused the AE. There is a temporal relationship between the event onset and the study procedure or device. There is strong mechanistic evidence that the event was caused by the study procedure or device. The subject's clinical state and concomitant therapies have been ruled out as a cause.

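### The AE recording rules conflict with one another and with the exit rule, so the safety objective in section 4.3 is only partly served

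*Combined protocol and SAP*

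**What the plan says.** All references are to the combined protocol and SAP.

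- **Objective.** Section 4.3 sets a general aim: "Characterize the safety profile of MIRODERM and the procedure". The synopsis (Study Objectives) is narrower and speaks only of tracking related events.
- **Exit.** When an infection is found at a follow-up visit, 6.7.2 asks for an AE form and then "the subject will be discontinued from the study". Section 6.9 lists infection or osteomyelitis of the study ulcer among the exit reasons and adds: "When a subject is study exited, patients are no longer considered participants in the study and have no further obligations under the protocol".
- **Content of the AE record.** Section 14.3: "Each AE record will include a description of the event, date of onset, date of resolution, severity, treatment as applicable, and relationship to study device". Section 6.10.7 gives much the same list.
- **What counts as an AE.** Section 14.1 says of an AE that "it does not necessarily have to have a causal relationship with the device or the procedure". SAEs are defined there as a subset of AEs, so they inherit this.
- **What is documented.** Section 14.2: "Likewise, reportable AEs will be limited to AEs which are 1) definitely related to, or 2) likely related to, the study wound or treatment". Section 14.3 applies the same limit to the AE form.
- **When AEs start.** Section 14.2: "only events that occur after MIRODERM treatment can be considered AEs". Section 6.6.3, at the treatment visit, says: "If an infection is present an AE form should be completed and" the subject is then discontinued.

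**The concern.** Section 5.1 names infection, cellulitis and osteomyelitis among the risks of treatment, and 5.3 presents a lower chance of infection and eventual amputation as a potential benefit. Yet infection is the event at which study follow-up stops. A reader of the final report would learn that an infection occurred, but the plan gives no means of learning how it ended.

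The relatedness limit raises a second problem. Relatedness would normally be a rating attached to a recorded event. Here it decides whether the event is recorded at all, and serious events are not exempt. Section 5.2 relies on AE tracking to pick up problems across the cohort, and a single-arm study has no control group against which a shortfall in recording might show up. Data not collected prospectively may be impossible to recover at analysis.

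**Working it through.** The plan gives no safety sample size, expected AE rate or infection rate, so there is no safety figure to reproduce. Its only precision figures are the exact intervals for the closure proportion at n = 50. These reproduce (at 50%: 35.53% to 64.47%, printed as 35.5% to 64.5%) but have no bearing on this point. The check is a comparison of sections.

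**1. Exit against the AE record (6.7.2 and 6.9 against 6.10.7 and 14.3).** The AE form is opened when the infection is found, and the subject is discontinued at that visit. Treatment and resolution of the infection will usually come later. No section describes a contact, visit or chart review after exit. Section 14.2 mentions follow-up information once, only as something sent to the IRB under that IRB's own policy; it does not say who obtains it or how. So the onset is recorded, while two required fields and any later hospitalisation or amputation have no collection route.

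**2. Definition against documentation (14.1 against 14.2 and 14.3).** Following each kind of event through the text:

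| Event after first application | Prescribed record |
|---|---|
| Rated likely or definitely related to study wound or treatment | AE form |
| Non-fatal SAE rated lower, no exit | None |
| Death rated lower | Discontinuation form only (6.9, 6.10.6) |

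Only two relatedness levels are defined, both in 14.3, and both refer to the procedure or device and not to the wound. The lower of the two, Likely, also excludes an event that the subject's clinical state readily explains. An infected diabetic foot ulcer can often be explained that way. An investigator applying 14.3 literally could therefore leave out a wound infection or osteomyelitis that 14.2 lists as reportable.

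**3. Start of the AE window (6.6.3 against 14.2).** At the treatment visit the infection check is in 6.6.3 and the first application is in 6.6.4. An infection found at that check precedes treatment. Section 6.6.3 requires an AE form for it; 14.2 says it cannot be an AE. Section 14.2 also lists debridement-related events as reportable without saying whether the Visit 1 debridement (6.5.7), which comes before the window opens, is meant.

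**4. Scope of the objective (synopsis against 4.3).** The synopsis covers related events only; 4.3 carries no such limit.

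**Size, by assumption only.** Let q be the share of subjects who exit for infection and w the week of exit.

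- Subjects with no prescribed later safety observation = q × n. For q = 5% to 30%: 0.05 × 50 = 2.5 to 0.30 × 50 = 15 at n = 50, and 0.05 × 65 = 3.25 to 0.30 × 65 = 19.5 at n = 65.
- Share of the 12-week window unseen for such a subject = (12 − w)/12. For w = 1, 4, 8: 11/12 = 92%, 8/12 = 67%, 4/12 = 33%.

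The second figure is a maximum, because a subject whose wound closes leaves one week after closure in any case.

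**The case against.** The strongest reply is that the plan does roughly what it promises. This is a post-market study of a cleared device; the synopsis limits the objective to related events, and 5.2 speaks in similar terms. The filter covers the study wound as well as the treatment, and 14.2 names cellulitis, osteomyelitis, wound infection, recurrence and ulcer enlargement. Deaths reach the discontinuation form. Section 6.9 releases the patient from obligations; it does not expressly release the investigator from completing an open AE form. Subjects come from the investigators' own practice and network, and section 9 gives access to medical records for verification. Debridement-related events make sense for debridements at follow-up visits (6.7.3), after the window has opened.

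Much of this stands, and it rules out the stronger readings. A reader might infer that the safety objective is not met at all, or that the plan abandons infected subjects. The documents do not support either: the index infection is recorded, a resolution date is required, and the narrower synopsis objective is largely served. A reader might also infer that a report of no later serious limb events would be an artefact of exit. That would need every such event to fall after exit and none to reach the treatment or resolution fields, which cannot be shown from the documents.

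The reply does not remove the conflicts. Access for verification is not a procedure for collecting outcomes. The list in 14.2 does not override the Likely definition in 14.3. Nothing exempts SAEs from the filter. The clash between 6.6.3 and 14.2 is plain on the page.

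**Conclusion.** The point holds as a set of conflicts that need reconciling, with the 4.3 objective only partly served. As written, the study will record infections but has no defined way to report how they ended once the subject has exited. It cannot give an overall AE or SAE rate, and a lower-rated non-fatal SAE may leave no trace. It also has two incompatible rules for an infection found just before the first application.

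The consequence cannot be sized from the documents, which give no infection rate, exit time or rate of limb events. The range of 2.5 to 15 subjects of 50 rests wholly on an assumed 5% to 30% of infection exits. The conflicts themselves rest on no assumption.

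**What to change.** Leave the exit rule as it is, and change the data rules around it:

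1. **6.9 and 14.3.** For each treated subject who exits with an open AE and has not withdrawn consent, record resolution, hospitalisation and amputation from the medical record or one telephone call, up to resolution or the date the 12-week visit would have fallen. Add matching wording to the consent form.
2. **14.2 and 14.3.** Record all SAEs, and all events on the 14.2 study-wound list, whatever their relatedness. Add relatedness categories below Likely, and make the definitions cover the study wound if the filter is to refer to it.
3. **6.6.3 and 14.2.** State one AE start point so that the two sections agree, and say whether the Visit 1 debridement is covered.
4. **Synopsis and 4.3.** Give the safety objective the same scope in both places.

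Cost: some extra data entry for unrelated SAEs, a chart review or call for a few subjects, revised AE form and protocol wording, and a consent change with IRB approval. Subjects already in the study may need to be re-consented under section 10.
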